### **SAE reporting to the Sponsor via paper CRF**

- Facsimile transmission of the SAE paper CRF is the preferred method to transmit this information to the Sponsor's representative.
- In rare circumstances and in the absence of facsimile equipment, notification by telephone is acceptable with a copy of the SAE data collection tool sent by overnight mail or courier service.
- Initial notification via telephone does not replace the need for the Investigator to complete and sign the SAE CRF pages within the designated reporting time frames.
- Contacts for SAE reporting can be found in the protocol.

## **10.4 APPENDIX 4: CONTRACEPTIVE GUIDANCE AND COLLECTION OF PREGNANCY INFORMATION**

### **DEFINITIONS:**

#### **Woman of childbearing potential (WOCBP)**

A woman is considered fertile following menarche and until becoming post-menopausal unless permanently sterile (see below).

If fertility is unclear (eg, amenorrhea in adolescents or athletes) and a menstrual cycle cannot be confirmed before first dose of study intervention, additional evaluation should be considered.

#### **Women in the following categories are not considered WOCBP**

1. Premenarchal
2. Premenopausal female with 1 of the following:

Documented hysterectomy  
Documented bilateral salpingectomy  
Documented bilateral oophorectomy

For individuals with permanent infertility due to an alternate medical cause other than the above, (eg, mullerian agenesis, androgen insensitivity), Investigator discretion should be applied to determining study entry.

Note: Documentation can come from the site personnel's: review of the participant's medical records, medical examination, or medical history interview.

3. Postmenopausal female
  - A postmenopausal state is defined as no menses for 12 consecutive months without an alternative medical cause.
  - Females on HRT and whose menopausal status is in doubt will be required to use one of the non-estrogen hormonal highly effective contraception methods if they wish to continue their HRT during the study.

## CONTRACEPTION GUIDANCE

Female participants of childbearing potential are eligible to participate if they agree to use a highly effective method of contraception consistently and correctly as described below.

---

### Highly effective contraceptive methods that are user dependenta

*Failure rate of <1% per year when used consistently and correctly.*

Combined (estrogen and progestogen containing) hormonal contraception associated with inhibition of ovulation

- Oral
- Intravaginal
- Transdermal

Progestogen only hormonal contraception associated with inhibition of ovulation

- Oral
- Injectable

---

### Highly effective methods that are user independenta

Implantable progestogen only hormonal contraception associated with inhibition of ovulation

- Intrauterine device
- Intrauterine hormone-releasing system
- Bilateral tubal occlusion

---

### Vasectomized partner

*A vasectomized partner is a highly effective contraception method provided that the partner is the sole male sexual partner of the WOCBP and the absence of sperm has been confirmed. If not, an additional highly effective method of contraception should be used.*

---

### Sexual abstinence

*Sexual abstinence is considered a highly effective method only if defined as refraining from heterosexual intercourse during the entire period of risk associated with the study intervention. The reliability of sexual abstinence needs to be evaluated in relation to the duration of the study and the preferred and usual lifestyle of the participant.*

---

#### NOTES:

a Typical use failure rates may differ from those when used consistently and correctly. Use should be consistent with local regulations regarding the use of contraceptive methods for participants participating in clinical studies.

## COLLECTION OF PREGNANCY INFORMATION:

### Male participants with partners who become pregnant

- The Investigator will attempt to collect pregnancy information on any male participant's female partner who becomes pregnant while the male participant is in this study. This applies only to male participants who receive dupilumab.
- After obtaining the necessary signed informed consent from the pregnant female partner directly, the Investigator will record pregnancy information on the appropriate form and submit it to the Sponsor within 24 hours of learning of the partner's pregnancy. The female partner will also be followed to determine the outcome of the pregnancy. Information on the status of the mother and child will be forwarded to the Sponsor. Generally, the follow-up will be no longer than 6 to 8 weeks following the estimated delivery date. Any termination of the pregnancy will be reported regardless of fetal status (presence or absence of anomalies) or indication for the procedure.

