## Overall design:

The master protocol EFC16461 will be comprised of 3 studies of similar design, 2 studies in participants who are omalizumab naïve (Study A and Study C) and 1 study in participants who are intolerant or incomplete responders to omalizumab (Study B). Study A and Study C will include adults, adolescents ( $\geq$ 12 to  $<$ 18 years) and children ( $\geq$ 6 to  $<$ 12 years in some selected countries). Study B will include adults and adolescents. The three studies are 24-week, double-blind, randomized, placebo-controlled studies to evaluate the use of dupilumab in participants with CSU who remain symptomatic despite the use of H1-AH. The studies will assess the effect of dupilumab on the itch and hives scored separately once daily and averaged over 7 days and on the

itch and hives frequency/severity through the urticaria activity score (composite) averaged over 7 days, on angioedema activity, urticaria control, and on patients' health-related quality-of-life (HRQoL), and health status.

**Disclosure statement:** Each Study A, B, and C is a Treatment study with 2 Parallel arms that is blinded/masked for participants and Investigators. While these are double blind trials with regard to the treatment with either dupilumab or placebo, they are not blinded to weight-based dose levels, due to the different volume size (2 mL versus 1.14 mL) of the dose level of dupilumab (300 mg/matching placebo or 200 mg/matching placebo) that will be used for the different weight categories for adolescents and children  $\geq 6$  to  $<12$  years of age. In addition, in children, the study is not blinded to dose regimen due to the different frequency of IMP administration (q4w versus q2w).

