### **Methods of blinding**

Dupilumab 300 mg/200 mg and placebo matching dupilumab 300 mg/200 mg will be provided in identically matched 2 mL/1.14 mL pre-filled syringes that are visually indistinguishable for each dose. Syringes and box will be labeled with a treatment kit number. While these are double-blind trials with regard to the treatment with either dupilumab or placebo, they are not blinded to weight based dose levels, due to the different volume size (2 mL versus 1.14 mL) of the dose level of dupilumab (300 mg/matching placebo or 200 mg/matching placebo) that will be used for the different weight categories for adolescents and children  $\geq 6$  to  $<12$  years of age. In addition, in children, the study is not blinded to dose regimen due to the different frequency of IMP administration (q4w versus q2w).

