### **8.3 ADVERSE EVENTS AND SERIOUS ADVERSE EVENTS**

#### **Adverse event of special interest**

An adverse event of special interest (AESI) is an AE (serious or nonserious) of scientific and medical concern specific to the Sponsor's product or program, for which ongoing monitoring and immediate notification by the Investigator to the Sponsor is required. Such events may require further investigation in order to characterize and understand them. Adverse events of special interest may be added, modified or removed during a study by protocol amendment.

For these AESIs, the Sponsor will be informed immediately (ie, within 24 hours), per SAE notification described in [Section 10.3](#), even if not fulfilling a seriousness criterion, using the corresponding pages in the CRF (to be sent) or screens in the e-CRF.

- Anaphylactic reactions
- Systemic hypersensitivity reactions
- Helminthic infections
- Any severe type of conjunctivitis or blepharitis
- Keratitis
- Clinically symptomatic eosinophilia (or eosinophilia associated with clinical symptoms)
- Significant ALT elevation
  - ALT  $>5 \times$  the ULN in participants with baseline ALT  $\leq 2 \times$  ULN;  
or
  - ALT  $>8 \times$  ULN if baseline ALT  $>2 \times$  ULN.
- Pregnancy of a female subject entered in a study as well as pregnancy occurring in a female partner of a male subject entered in a study with IMP/non-investigational medicinal product (NIMP)
  - Pregnancy occurring in a female participant entered in the clinical trial or in a female partner of a male participant entered in the clinical trial. It will be qualified as an SAE only if it fulfills 1 of the seriousness criteria
  - In the event of pregnancy in a female participant, IMP should be discontinued.
  - Follow-up of the pregnancy in a female participant or in a female partner of a male participant is mandatory until the outcome has been determined.
  - Abnormal pregnancy outcomes (eg, spontaneous abortion, fetal death, stillbirth, congenital anomalies, ectopic pregnancy) are considered SAEs.

- Symptomatic overdose (serious or nonserious) with IMP/NIMP
  - An overdose (accidental or intentional) with the IMP is an event suspected by the Investigator or spontaneously notified by the participant and defined as at least twice the intended dose during an interval of less than 11 days. The circumstances (ie, accidental or intentional) should be clearly specified in the overdose form.

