### **8.3.5 Pregnancy**

- Details of all pregnancies in female participants and female partners of male participants will be collected after the start of study intervention and up to the EOS Visit or within 12 weeks after last study intervention, whichever was later.
- If a pregnancy is reported, the Investigator should inform the Sponsor within 24 hours of learning of the pregnancy and should follow the procedures outlined in Appendix 4 ([Section 10.4](#)).
- Abnormal pregnancy outcomes (eg, spontaneous abortion, fetal death, stillbirth, congenital anomalies, ectopic pregnancy) are considered SAEs.

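### Appendix 4 limits partner-pregnancy collection to men who receive dupilumab, which conflicts with Sections 8.3 and 8.3.5 and cannot be applied under the blind

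*Protocol*

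**What the plan says.** Four parts of the protocol deal with pregnancies in partners of male participants, or with who may know the treatment arm.

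- **Section 10.4 (Appendix 4), male participants with partners who become pregnant.** The bullet opens without an arm limit: "The Investigator will attempt to collect pregnancy information on any male participant's female partner who becomes pregnant" while the man is in the study. It ends with one: "This applies only to male participants who receive dupilumab". The next bullet gives the investigator 24 hours from learning of the pregnancy to submit the form, once the partner has consented.
- **Section 8.3, adverse events of special interest.** The list includes "pregnancy occurring in a female partner of a male subject entered in a study with IMP/non-investigational medicinal product (NIMP"). AESIs must reach the sponsor within 24 hours. Follow-up of a pregnancy in a female participant or "in a female partner of a male participant is mandatory until the outcome has been determined".
- **Section 8.3.5.** "Details of all pregnancies in female participants and female partners of male participants will be collected after the start of study intervention". The window closes at the end-of-study (EOS) visit or 12 weeks after the last study intervention, whichever is later. When a pregnancy is reported, sites are sent to Appendix 4 for the procedures.
- **Blinding.** The synopsis describes each study as having "2 Parallel arms that is blinded/masked for participants and Investigators". Section 6.3 calls them "double-blind trials with regard to the treatment with either dupilumab or placebo". The open elements are weight-based dose level and, in children, dosing frequency.

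**The concern.** The restriction depends on something the investigator is not allowed to know. A site that learns of a partner pregnancy and turns to Appendix 4 finds a rule that applies to one arm only, and nothing in the protocol says which section prevails over another. The site can disregard the sentence, hold back or omit the record, or seek the allocation. Only the first is harmless, and it means setting protocol text aside.

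What is at stake is the evenness of safety data collection. All three SAPs take the pregnancy AESI from the participant-pregnancy and partner-pregnancy boxes on the eCRF, and they plan risk differences and hazard ratios for each AESI (Section 4.7.2). An event type recorded in one arm only cannot be described against a control.

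**Working it through.** No arithmetic underlies the main point. The check is to set the passages side by side, ask whether the restriction can be carried out, and trace what the data feed into.

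**1. Scope of collection**

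| Place in the protocol | Whose partners | Arm limit |
|---|---|---|
| Section 8.3, AESI list | Male subjects entered in the study | None |
| Section 8.3, follow-up duty | Male participants | None |
| Section 8.3.5, first bullet | Male participants | None |
| Appendix 4, opening of the bullet | Any male participant | None |
| Appendix 4, end of the bullet | Men who receive dupilumab | Dupilumab only |

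Four statements agree and one does not. The odd one out is current appendix text, not amendment history.

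**2. Can a blinded investigator apply it?** The syringe volume shows the dose level and, in children, the schedule shows the dosing frequency. Each dose level and regimen has a matching placebo, so neither shows the arm. Section 6.3 describes the investigator's code break for an emergency, and Section 7.1.1 says that a break requested by the investigator leads to permanent discontinuation of study intervention. There is therefore no ordinary route by which a site could learn whether the restriction applies.

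**3. What would be lost if it were applied?** The AESI selection tables (Table 8 in the Study A and Study B SAPs, Table 7 in the Study C SAP) put pregnancy in a female participant and pregnancy in a male participant's partner in one row. The Appendix 4 text on female participants has no arm limit. On a literal reading, then:

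- participant pregnancies are recorded in both arms;
- partner pregnancies are recorded in the dupilumab arm only.

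Only the second component of the row becomes one-sided. Section 4.7 of each SAP states that the safety analysis is essentially descriptive, with no testing planned.

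**4. Collection window.** The two places also differ on time. Appendix 4 covers the period while the man is in the study. Section 8.3.5 runs to EOS or 12 weeks after the last study intervention, whichever is later. For a man on two-weekly dosing who completes, the planned last dose is at Week 22, so 12 weeks later is 22 + 12 = Week 34. EOS is at 24 + 12 = Week 36, so both windows end at EOS. They part for a man who leaves the study less than 12 weeks after his last dose: Appendix 4 stops at withdrawal, while Section 8.3.5 runs on to 12 weeks after the dose.

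**5. Which studies are affected?** Study A is complete. Study B has finished recruiting (108 randomized), and treatment is being stopped with follow-up continuing. Study C, with about 150 to be randomized, is where new participants will be enrolled under this text. The documents give neither the number of men nor a partner-pregnancy rate, so no expected count can be derived.

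**The case against.** The best defence is that the operative rule is already right. Section 8.3.5 sets the scope in its first bullet and sends sites to Appendix 4 only for procedures once a pregnancy is reported, so the main text does not hand the scope over to the appendix. Section 8.3 makes notification and follow-up mandatory. A blinded investigator who cannot tell whether the restriction applies has an obvious default, which is to collect for everyone. This largely stands: most sites would probably collect from both arms. It makes the harm a risk rather than a certainty, but it does not remove the contradiction.

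Two stronger readings are tempting, and the documents do not support either.

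- A reader might infer that the pregnancy AESI would have no control data. It would still have some: the row combines participant and partner pregnancies, and the former are collected in both arms.
- A reader might infer that the appendix forces unblinding, and with it discontinuation of study intervention. Deciding whether to complete a pregnancy form is not the emergency that Section 6.3 describes, and an investigator would have to pass over several unrestricted instructions before getting there. A code break by this route is a remote possibility.

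It could also be said that the restriction is meant as a filter after unblinding. The text does not say so. It addresses the investigator, whose form is due within 24 hours, and a later filter would still conflict with Sections 8.3 and 8.3.5.

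**Conclusion.** The point holds as a minor internal inconsistency. The last sentence of the Appendix 4 bullet contradicts the bullet's own opening, Section 8.3 and Section 8.3.5, and it cannot be carried out while the investigator is blinded.

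The most that can follow is a partner-pregnancy component without placebo-arm records, inside a descriptive AESI summary. Pregnancies in female participants, the efficacy analyses, the type I error rate and the sample size are unaffected. That the number of records at risk is small is a judgement, because the documents supply no rate. The practical effect is mainly on Study C, with a residual effect on men still in follow-up in Study B. The conclusion assumes that some site might act on the literal wording; where every site follows Sections 8.3 and 8.3.5, nothing is lost.

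**What to change.** Delete from Appendix 4 the sentence "This applies only to male participants who receive dupilumab", so that partner-pregnancy information is collected in the same way in both arms, as Sections 8.3 and 8.3.5 already require. Collection regardless of arm is also the only version that can be followed under the blind.

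In the same edit, replace Appendix 4's in-study window with the one in Section 8.3.5 (EOS or 12 weeks after the last study intervention, whichever is later), so that a site following either place collects over the same period.

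The cost is a one-sentence deletion, a short wording change and at most a few extra pregnancy follow-up forms. The SAPs need no change, since their AESI definition already covers partner pregnancy without reference to arm.

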## Female participants who become pregnant

[figure not shown]
- The Investigator will collect pregnancy information on any female participant who becomes pregnant while participating in this study. Information will be recorded on the appropriate form and submitted to the Sponsor within 24 hours of learning of a participant's pregnancy. The participant will be followed to determine the outcome of the pregnancy. The Investigator will collect follow-up information on the participant and the neonate and the information will be forwarded to the Sponsor. Generally, follow-up will not be required for longer than 6 to 8 weeks beyond the estimated delivery date. Any termination of pregnancy will be reported, regardless of fetal status (presence or absence of anomalies) or indication for the procedure.
- Any pregnancy complication or elective termination of a pregnancy will be reported as an AE or SAE. A spontaneous abortion is always considered to be an SAE and will be reported as such. Any post-study pregnancy related SAE considered reasonably related to the study intervention by the Investigator will be reported to the Sponsor as described in [Section 8.3.4](#) of the protocol. While the Investigator is not obligated to actively seek this information in former study participants, he or she may learn of an SAE through spontaneous reporting.
- Any female participant who becomes pregnant while participating in the study will discontinue study intervention.

## 10.5 APPENDIX 5: GENETICS

- **Use/Analysis of DNA and RNA**
- Genetic variation may impact a participant's response to study intervention, susceptibility to, and severity and progression of disease. Variable response to study intervention may be due to genetic determinants that impact drug absorption, distribution, metabolism, and excretion; safety, mechanism of action of the drug; disease etiology; and/or molecular subtype of the disease being treated. Therefore, where local regulations and IRB/IEC allow, a blood sample will be collected for DNA analysis from consenting participants.
- DNA and RNA samples will be used for research related to dupilumab or chronic spontaneous urticaria and related diseases. They may also be used to develop tests/assays including diagnostic tests related to dupilumab or related drugs and atopic/allergic diseases. Genetic research may consist of the analysis of 1 or more candidate genes or the analysis of genetic markers throughout the genome [including whole-exome sequencing, whole-genome sequencing, and DNA copy number variation. Transcriptome sequencing (or other methods for quantitating RNA expression) may also be performed.
- The samples may be analyzed as part of a multi-study assessment of genetic factors involved in the response to study intervention or study interventions of this class to understand study disease or related conditions.
- The Sponsor will store the DNA and RNA samples in a secure storage space with adequate measures to protect confidentiality.
- The samples will be retained while research on study intervention or study interventions of this class or indication continues but no longer than 15 years or other period as per local requirements.

## 10.6 APPENDIX 6: LIVER AND OTHER SAFETY: SUGGESTED ACTIONS AND FOLLOW UP ASSESSMENTS

### INCREASE IN ALT

**In ANY CASE, FOLLOW** the instructions listed in the box below:

1. **INFORM** the Site Monitor who will forward the information to the Study Manager
2. **INVESTIGATE** specifically for malaise with or without loss of consciousness, dizziness, and/or hypotension and/or episode of arrhythmia in the previous 72 hours; rule out muscular injury
3. **PERFORM** the following tests:
  - LFTs: AST, ALT, alkaline phosphatase, total and conjugated bilirubin and prothrombin time / INR
  - CPK, serum creatinine, complete blood count
  - Anti-HAV IgM, anti-HBc IgM (HBV-DNA if clinically indicated), anti-HCV and HCV RNA, anti-CMV IgM and anti-HEV IgM antibodies
  - Depending on the clinical context, check for recent infection with EBV, herpes viruses, and toxoplasma
  - Hepatobiliary ultrasonography (or other imaging investigations if needed)
4. **CONSIDER** Auto-antibodies: antinuclear, anti-DNA, anti-smooth muscle, anti-LKM
5. **CONSIDER** consulting with hepatologist
6. **CONSIDER** patient hospitalisation if INR>2 (or PT<50%) and/or central nervous system disturbances suggesting hepatic encephalopathy
7. **MONITOR LFTs after discontinuation of IMP:**
  - As closely as possible (or every 48 hours) until stabilization, then every 2 weeks until return to normal/baseline or clinical resolution.
8. **FREEZE** serum sample (5ml x 2)
9. **In case of SUSPICION of GILBERT Syndrome**, a DNA diagnostic test should be done

\*If unable to retest in 72 hours, use original laboratory results to decide on further reporting/monitoring/discontinuation.

[figure not shown]
Note:

“Baseline” refers to ALT sampled at Baseline Visit; or if baseline value unavailable, to the latest ALT sampled before the Baseline Visit. The algorithm does not apply to the instances of increase in ALT during screening.

See [Section 10.3](#) for guidance on safety reporting.

Normalization is defined as  $\leq$ ULN or baseline value, if baseline value is  $>$ ULN.

[figure not shown]
**INCREASE IN CPK OF NON-CARDIAC ORIGIN AND NOT  
RELATED TO INTENSIVE PHYSICAL ACTIVITY**

Increase in CPK is to be recorded as an AE only if at least 1 of the criteria in the general guidelines for reporting adverse events in [Section 10.3](#) is met.

